All potential participants will be evaluated at the Substance Use and Research Center (SURC) at the New York Psychiatric Institute.

How and by whom will subjects be approached and/or recruited?

All patients will be seen by one of our psychiatrists or psychologists for a screening evaluation and mental status examination as part of routine admission procedures. Patients who are opioid dependent and appear to meet criteria are told about the study and offered further evaluation. Final informed consent for the study will be obtained after full psychiatric and medical workup is complete. Procedures for training staff physicians in each protocol and consent form include initial presentations by the Principal Investigator at weekly staff meetings, and weekly discussion of inclusion/exclusion criteria and study eligibility for each screening participant.

How will the study be advertised/publicized?

Once approved by the IRB, advertisements for the study will be placed in local newspapers and radio stations. Additionally, prospective participants are recruited by word of mouth through liaison to other local clinical services.

Do you have ads/recruitment material requiring review at this time?

No

Does this study involve a clinical trial?

Yes

YOU MUST REGISTER AT ClinicalTrials.gov IMMEDIATELY UPON RECEIPT OF IRB APPROVAL AND **PRIOR TO ENROLLMENT** OF THE FIRST SUBJECT. YOU WILL BE PROVIDED WITH A NCT REGISTRATION NUMBER ON REGISTRATION. PLEASE REVISE THIS SECTION OF THE PROTOCOL SUMMARY FORM TO INCLUDE THE NCT NUMBER AND RE-SUBMIT AS AN AMENDMENT TO THE IRB.

Concurrent Research Studies

Will subjects in this study participate in or be recruited from other studies?

No

Inclusion/Exclusion Criteria

Name the subject group/sub sample

Adult heroin users who meet criteria for current opioid use disorder

Create or insert table to describe the inclusion criteria and methods to ascertain them

1. Individuals between the ages of 18-60 (clinical interview)

2. Meets DSM-5 criteria of current opioid use disorder with six consecutive months of reported heroin use, supported by a positive urine for opiates indicating regular use of heroin

3. Seeking treatment for opioid use disorder with Vivitrol (Clinical interview)
4. Capable of giving informed consent and complying with study procedures (clinical interview)

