5. In otherwise good health based on complete medical history and physical examination, laboratory tests, and EKG (Medical history and physical examination by psychiatrist, laboratory tests (serum Chem-20 and CBC, urinalysis) ECG)
6. BMI between 18-40 (clinical interview, vitals)

Create or insert table to describe the exclusion criteria and methods to ascertain them

- 1) Reported treatment with methadone in the last 3 months or positive urine toxicology for methadone on the day of consent (clinical interview)
- 2) Maintenance on, or regular use of buprenorphine or other prescription opioids (clinical interview)
- 3) Pregnancy, lactation, or failure in a sexually active woman to use adequate contraceptive methods. (Clinical interview by psychiatrist and medical history by psychiatrist, urine pregnancy test, serum HCG)
- 4) Active medical illness which might make participation hazardous, such as untreated hypertension, acute hepatitis with AST or ALT > 3 times normal, AIDS (CD4 count under 200 currently or medically ill with an opportunistic infection), unstable diabetes, cardiovascular disease. (medical history and physical examination by psychiatrist, laboratory tests: serum Chem-20 and CBC, urinalysis, ECG)
- 5) Active psychiatric disorder which might interfere with participation or make participation hazardous, including DSM-5 Schizophrenia or any psychotic disorder, severe Major Depressive Disorder, or suicide risk or 1 or more suicide attempts within the past year. (MINI interview by therapist, clinical interview and mental status exam by psychiatrist, contact with collateral information as needed and available).
- 6) Physiologically dependent on alcohol or sedative- hypnotics with impending withdrawal. Other substance use diagnoses are not exclusionary. (MINI interview by therapist, Clinical interview by psychiatrist)
- 7) History of allergic or adverse reaction to buprenorphine, naltrexone, naloxone, clonidine, or clonazepam. (Clinical interview by psychiatrist)
- 8) Chronic **neurocognitive disorder** (Clinical interview by psychiatrist)
- 9) History of accidental drug overdose in the last 3 years as defined as an episode of opioid-induced unconsciousness or incapacitation, whether or not medical treatment was sought or received. (MINI interview by therapist, clinical interview by psychiatrist)

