- 10) Painful medical condition that requires ongoing opioid analgesia or anticipated surgery necessitating opioid medications (Clinical interview psychiatrist)

- 11) Fentanyl only use, supported by a urine toxicology that is positive for fentanyl only and negative for all other opioids. (Clinical interview, urine toxicology)
- 12) Court mandated to treatment (clinical interview)

Waiver of Consent/Authorization

Indicate if you are requesting any of the following consent waivers

Waiver of consent for use of records that include protected health information (a HIPAA waiver of Authorization)

No

Waiver or alteration of consent

No

Waiver of documentation of consent

No

Waiver of parental consent

No

Consent Procedures

Is eligibility screening for this study conducted under a different IRB protocol?

No

Describe procedures used to obtain consent during the screening process

Potential participants will sign the **screening consent page of the study consent** form prior to initiating the screening process. Following review of screening informed consent, an evaluation team consisting of a Masters level research psychologist and psychiatrist meets with potential participants. The baseline evaluation includes a full battery of self-report measures, a structured psychiatric evaluation (MINI interview), Hamilton depression scale, a physical examination, and laboratory assessments. Medical screening and laboratory work, include vital signs, a physical examination, ECG, serum chemistry, liver function tests, complete blood count, and urinalysis obtained by study personnel. Pregnancy tests will be conducted for women.

Describe Study Consent Procedures

After the screening evaluation, the study physician will review the study inclusion/exclusion criteria to determine if the participant is eligible for the study based on the screening materials. If the participant is eligible for the study, they will be given the consent form to read, and review with the consenting physician. The study consent will only be signed after all of the participant's questions are asked, and after all the risks and benefits are explained to and understood by the participant. Study related procedures will only be initiated after the consent form is signed by both the participant and consenting physician.

Indicate which of the following are employed as a part of screening or main study consent procedures

Consent Form

Persons designated to discuss and document consent

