Select the names of persons designated to obtain consent/assent

[name], MD

Type in the name(s) not found in the above list

Study Procedures

Describe the procedures required for this study

Buprenorphine induction/stabilization/taper: Buprenorphine induction will be conducted at the SURC center. After consenting to the study, participants will receive buprenorphine, dispensed weekly, that they will take daily. Participants will be stabilized on, and tapered off, buprenorphine over a 3-week period. Reductions will occur in a graded fashion, with the stabilization dose reduced to 4mg, according to the following schedule:

- **Day 0 (Study Consent + ancillary medications).** Participants will be advised to abstain from opioids for at least 12-16 hours prior to taking their first dose of buprenorphine/naloxone in the clinic the next day.
- **Day 1:** After a COWS of 6-10, participants will receive buprenorphine/naloxone 2/0.5mg. If tolerated, the patient will receive an additional 4mg onsite, with 2mg to take home that evening. Patients will receive a total of 8/2mg on Day 1.
- **Days 2-7:** 8/2 mg buprenorphine/naloxone
- **Days 8-14:** 6/1.5 mg buprenorphine/naloxone
- **Days 15-21:** 4/1 mg buprenorphine/naloxone

Participants will attend the center twice weekly and will be assessed for opioid and other substance use (urine toxicology and self-report), vital signs, opioid withdrawal symptoms, opioid cravings, and dose adjustments of buprenorphine will be made as needed by study physicians. This approach to buprenorphine taper is intended to resemble standard clinical practice, in which patients seeking transition off buprenorphine undergo a slow taper. The purpose is in part to provide a slow transition with minimal withdrawal symptoms. Participants will have at least two study visits a week during the buprenorphine taper, but may be seen more regularly at the center if deemed clinically necessary. Participants will be required to submit at least one opioid negative urine (except for buprenorphine) during the last two weeks of the buprenorphine taper. **Participants who are not able to submit at least one opioid negative urine**

during the last two weeks of the buprenorphine taper will be offered buprenorphine to resume in the clinic and will be provided with referrals.

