Participants will be seen in the center twice weekly during the buprenorphine stabilization phase and daily on weekdays during the induction phase (Days 1-5). Once XR-NTX has been administered, participants will continue to be seen at the center twice weekly for 12 weeks. At each visit the patient will meet with the research assistant to complete research ratings. Research nurse collects safety measures and inquires about side effects. Side effects of study medications are reviewed weekly during the visit with a research psychiatrist, or more frequently if clinically indicated, and study psychiatrist will adjust medication dose if necessary.

At each visit the patient meets with the research assistant to complete research ratings, including self-report of withdrawal, mood, and drug use. The patient provides a urine sample under observation by a staff member at each visit. The sample is tested immediately for opiates with the iScreen system (Instant Technologies, Inc.). Vital signs are also taken. All data are then brought to the therapist and therapy session is held.

Participants may come to the center to be seen as frequently as needed. In particular, any participant who is experiencing protracted opioid withdrawal will be offered clinical contact on a frequent, even daily, basis. For clinical matters arising in the evenings or on weekends, participants will have access to the 24-hour emergency telephone service, staffed by physicians familiar with this protocol who can address patients' concerns.

Behavioral Therapy

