Participants may be also removed from the trial if they repeatedly miss scheduled appointments or clinical worsening necessitates more intensive treatment (drop out criteria are defined above). Subjects who develop serious psychiatric symptomatology (e.g. psychosis, suicidal ideation, severe depressive symptoms) during the study period will be dropped from the study and appropriate clinical referrals will be made. This would include, but not be limited to, patients who become unconscious after using, engage in destructive or violent behavior while intoxicated, report driving while intoxicated, or develop medical complications from their opioid use. In all cases where subjects are discontinued from the study, the clinical research staff will assume clinical responsibility for the subjects until clinical referrals are operational.

In the case that the patient is removed from the research trial for medical reasons, or is requesting withdrawal from the study, he/she will be retained in open treatment for the remaining study period. Upon removal of a patient from the trial due to clinical deterioration, the patient will be referred for appropriate follow-up treatment, in the most instances either intensive outpatient or residential treatment. The PI or a study psychiatrist is available 24 hours/day by phone and/or beeper in case of emergency.

If a patient is discontinued from the study, or decides to withdraw, or relapses during study participation, the patient will get treated with buprenorphine until they are linked with a referral for continuing buprenorphine treatment. Participants will receive a one-week supply of buprenorphine at a time during the transition process.

Buprenorphine will be also offered to participants if they are unable to continue with Vivitrol treatment at the end of the study. If additional injections of Vivitrol are available, they will also be offered to patients at the end of the treatment study.

Blood and other Biological Samples

Please create or insert a table describing the proposed collection of blood or other biological specimens. Urine samples will be collected at every visit, and we will use onsite testing to provide immediate feedback on opiate use to the participant and the treatment team. Blood chemistry will be obtained at baseline and end of study. Urine pregnancy tests will be obtained at baseline and prior to each administration of XR-NTX.

Assessment Instruments

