Buprenorphine Stabilization and Induction onto Vivitrol for Heroin-dependent Individuals

Statistical Analysis Plan

August 17, 2017

Primary objective

Individuals dependent on heroin have low rates of successful transition onto the Vivitrol on an outpatient basis. We propose to evaluate novel procedure to initiate treatment with Vivitrol in this difficult to treat population. Participants will be stabilized on buprenorphine for three weeks followed by a rapid induction onto Vivitrol using escalating doses of oral naltrexone.

Primary Endpoint

The primary outcome measure will be the proportion of patients successfully retained to receive the first naltrexone injection (dichotomous).

Secondary Objective

It is not known which factors predict, mediate, and moderate treatment response. Therefore, we propose to collect additional measures that may reflect the physiological changes associated with opioid withdrawal and naltrexone induction as well as response to medications. We will also evaluate the impact of concurrent substance use on treatment outcome and finally evaluate the safety of proposed protocol

Secondary Endpoint

Secondary Outcomes: 1) The proportion of patients successfully retained to receive second and third Vivitrol injection (dichotomous); 2) Measures of opiate withdrawal and sleep (continuous, longitudinal); 3) Measures of mood and anxiety (continuous, longitudinal); 4) Adverse events and serious adverse events; 5) A summary measure (combining urine and self-report) reflecting urine-confirmed abstinence from opioids and urine-confirmed abstinence from other drugs.

Exploratory Objectives

We will explore which patients are most likely to benefit from this procedure. We will evaluate the feasibility and acceptability of the protocol. We will evaluate whether proposed doses of adjunctive medications are adequate.

Hypothesis

We hypothesize that a short-term treatment with buprenorphine prior to initiating treatment with naltrexone will increase the proportion of heroin-dependent patients successfully inducted onto Vivitrol. We hypothesize that at least 65% of patients will be successfully retained to receive the first naltrexone injection. Based on our experience with various induction methods a response rate of less than 45% is too low to warrant further study of this treatment approach.

Analysis Plan

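### Does secondary outcome 5, urine-confirmed abstinence from opioids and other drugs, fail because the only assay named for each visit is an opiate test?

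*Protocol*

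**What the plan says.** The SAP, under Secondary Endpoint, lists as its fifth item a summary measure built from urine and self-report, "reflecting urine-confirmed abstinence from opioids and urine-confirmed abstinence from other drugs". It names no assay, no drug classes and no rule for combining the two sources.

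The protocol describes urine testing in several places:

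- **Study Visits:** an observed urine sample and a self-report of drug use at each visit, and "The sample is tested immediately for opiates with the iScreen system (Instant Technologies, Inc".
- **Blood and other Biological Samples:** urine at every visit, where "we will use onsite testing to provide immediate feedback on opiate use to the participant and the treatment team".
- **Study Procedures, buprenorphine taper:** at twice-weekly visits participants "will be assessed for opioid and other substance use (urine toxicology and self-report". The same paragraph requires at least one opioid-negative urine, with buprenorphine excepted, in the last two weeks of the taper.
- **Naltrexone induction and Procedures for Missed Doses of Vivitrol:** suspected relapse is tied to reported opioid use or a urine drug screen positive for opioids.
- **Assessment Instruments:** one urine toxicology entry, with its frequency given for stabilization, induction and post-induction together.

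Analytes are separated only at eligibility. Inclusion criterion 2 is "supported by a positive urine for opiates indicating regular use of heroin". Exclusion criterion 1 includes "positive urine toxicology for methadone on the day of consent". Exclusion criterion 11 is "Fentanyl only use, supported by a urine toxicology that is positive for fentanyl only and negative for all other opioids". Exclusion criterion 6 adds that "Other substance use diagnoses are not exclusionary".

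**The concern.** At eligibility the protocol treats opiates, methadone and fentanyl as distinct results, and exclusion 11 recognises a urine that is positive for fentanyl and negative for every other opioid. If the visit test is a narrow opiate test, that same urine would read as negative during follow-up. Only fentanyl-only users are excluded, so people who use both heroin and fentanyl can enrol. Other substance use is also allowed, so abstinence from other drugs is an outcome that can vary.

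A wide panel raises the opposite difficulty. Participants are given buprenorphine during the taper. They also receive clonazepam, a benzodiazepine, during washout and induction, with take-home ancillary doses for a week after the injection. Without a rule for these, prescribed medication could be counted as drug use.

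Two analysts could therefore score the same participant differently, with abstinence overstated on one reading and understated on the other. In a single-arm study reported mainly by descriptive statistics, the definition determines what the reported figure means.

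**Working it through.** There is no stated figure to reproduce, and the question turns on no error rate, power or effect size. The check is a comparison of texts, followed by the only arithmetic the documents allow.

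**1. Is the visit test shown to be limited to opiates?**

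| Place | Scope of testing as described |
|---|---|
| Study Visits | Opiates, tested immediately with a named kit |
| Blood and other Biological Samples | Immediate feedback on opiate use |
| Study Procedures, taper | Opioids and other substances, by urine and self-report |
| Study Procedures, taper urine requirement | Opioids, with buprenorphine considered separately |
| Naltrexone induction; Missed Doses | Drug screen for opioids |
| Assessment Instruments | Toxicology urine, one entry for all phases |
| Exclusion 11 | Fentanyl separated from all other opioids |

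Two places use the narrower word. Both concern the immediate onsite result, and the second gives its purpose as feedback. Neither says how outcome 5 is scored. The remaining places use wider wording. The protocol also uses the narrower word generically elsewhere: its sections on treatment alternatives and risks speak of opiate dependence and opiate withdrawal where the whole class is meant. The natural reading is one toxicology procedure throughout, described most fully in the taper paragraph. Nothing says it shrinks later.

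**2. What would the fentanyl error require?** Four things together:

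- the kit misses fentanyl;
- the kit result, and no wider toxicology, scores the outcome;
- the participant gives a sample containing fentanyl and no other detectable opioid;
- the participant does not report the use.

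The documents establish none of the four. Self-report is taken at each visit and is part of the outcome, and inclusion criterion 2 selects people whose urine is positive for opiates.

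**3. Can the scoring rule be supplied?** The outcome is called urine-confirmed and combines two sources, so the ordinary rule is that a visit counts as abstinent when urine is negative and self-report agrees. For buprenorphine, the taper paragraph already makes the needed exception. For clonazepam, the weekly Concomitant Medications Form in Assessment Instruments gives a record against which a positive can be read.

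**4. Do visit counts give a size?**

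- Buprenorphine phase: 2 per week × 3 weeks = 6.
- Induction: 5 (Days 1-5 in Study Visits).
- After the first injection: 2 × 12 weeks = 24 by Study Visits. By the end-of-study section, 4 weeks to the second injection + 4 weeks (28 days) = 8 weeks, so 2 × 8 = 16.
- Totals: 6 + 5 + 16 = 27, or 6 + 5 + 24 = 35.
- Visits outside the taper phase: 21/27 = 77.8%, or 29/35 = 82.9%.

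These shares count visits outside the phase where one explicit sentence on other substances appears. They do not count visits without testing, and they measure no error. The denominator is itself unsettled: the compensation section's maximum of $1,720 at $40 per visit implies 1,720/40 = 43 paid visits, which matches neither total.

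**The case for a change.** The strongest case for a change is that either reading leaves the outcome undefined. A narrow kit misses fentanyl and other drugs, and a wide panel picks up study-supplied medication. The explicit statement on other substances is confined to the buprenorphine phase, and the specimen section, where the form asks for a table, lists no analytes. The same unspecified panel lies behind the opioid-negative urine required before naltrexone induction, so it could influence who proceeds. Writing the panel down would cost little because the urine is already collected.

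Part of this stands. The panel, the assay that scores the outcome and the combination rule are not written, and the documents do not say whether later urines are read for fentanyl. Buprenorphine supplied after relapse, failed naloxone challenges or discontinuation is a further case with no stated scoring.

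The step from unwritten to deficient does not stand. The taper requirement is worded for opioids with buprenorphine excepted, which fits poorly with a test limited to opiates. The taper and relapse provisions are unspecific about the panel, but they do not contradict each other, and their use is clinical management separate from the scoring of outcome 5. Prescribing a wider panel would assume a shortfall that nobody has shown. If the existing panel is already wide, listing it would alter no measurement.

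**Conclusion.** No change to the plan follows. This is missing detail that the study's analysts can fill sensibly: use the toxicology result for all non-study opioids and other drug classes, require self-report to agree, and set aside positives explained by recorded study medication.

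The consequence is confined to one of five secondary items. It is descriptive, with no test or threshold attached, in a single-arm study planned around 30 completers. The primary endpoint is whether the first injection was given, which is not scored from urine. No bias in any reported figure is shown, and neither its size nor its direction can be derived from the documents.

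The conclusion assumes that the toxicology described in the taper paragraph is the procedure used throughout, as the single entry in Assessment Instruments suggests. The documents do not say what the named kit detects. If it proved narrow and were the sole basis for scoring, the reported measure would need to be described as abstinence from opiates.
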